12.1 Primary outcome variables

ORR (CR or PR), CBR (CR, PR or SD) and irORR (irCR or irPR) will be reported as the proportion of subjects of all efficacy evaluable subjects within each tumour type cohort and dosing regimen, both at cycle 4 and at cycle 7. The 90% confidence intervals for ORR, CBR and irORR will be calculated. Results from each tumour type (disease group) will be reported separately. There has been

recent debate about the definition of CBR and DCR. Recent article (“Clinical endpoints in oncology - a primer” by Delgado and Guddati) described that for CBR the SD should last at least 6 months. For clarity, and in order to comply with study protocol the tumour imaging results according the RECIST 1.1 will be presented by cycles (doing so there is no difference in the definition of DCR and CBR). Additionally, we are reporting the duration of SD to capture also that utility.

It should be noted that although the protocol states that irORR should be evaluated, it requires confirmation of irCR or irPR from an additional tumour evaluation carried out at least 4 weeks after irCR or irPR was established. However, due practical limitations in the population of subjects recruited for this study, the additional tumour evaluation could not be carried out on several occasions (only single PR result so far) and for this reason, ancillary information (e.g., no signs of clinical progression) will be reported for patients who continue treatment beyond PD.

When progression occurs, patients can continue treatment if IMP still is judged beneficial for the patient, i.e., clinical status does not indicate progression. This will be summarized using the following categories:

- No evidence of progression
- Evidence of progression, IMP still beneficial
- Evidence of progression, patient withdrawn

This presentation will be done for the first tumor imaging and first time of progression for the DCR subjects. Also, the confirmation image result will be reported for patients continuing IMP beyond progression.

Simon’s Two-Stage design will be used to evaluate efficacy and decide whether the cohort can be further expanded or not for Part III. The expansion of each disease group cohort is based on CBR (at cycle 4 or at cycle 7 for the Q3W dosing regimen) and the required proportion to proceed to Part III is 1/10. The same definition, CBR at cycle 4 or at cycle 7, will be used for the classification of subjects (DCR vs non-DCR) in the analyses.

12.2 Secondary outcome variables

Monocytes CLEVER-1 positivity: The proportion of CLEVER-1-positive monocytes in the blood total monocyte population will be measured by flow cytometry from blood samples collected over time during the first four cycles. Results will be reported with descriptive statistics. Also explorative statistical analyses will be conducted for the flow cytometry data, if feasible. Planned analytes for this are:

- Clever-1 anti-FP-1305 MFI
- Clever-1 anti-9-11 MFI
- Clever-1 anti-FP-1305 % of cells
- Clever-1 anti-9-11 % of cells
- CyTOF
- Response to LPS
- Anti-PD-1 MFI
- Anti-CTLA-4 MFI

S-CLEVER-1: S-CLEVER-1 and its occupancy by FP-1305 in the blood will be measured by immunoassay over time during the first cycles. Results will be reported with descriptive statistics. Also explorative statistical analyses will be conducted for the data, if feasible.

Pharmacokinetic Parameters: The serum concentration of FP-1305 will be determined by a validated method according to the assessment schedules. The concentrations will be summarized by visit and the sampling time using descriptive statistics by the dose level. Only subjects who have

received the whole dose at each infusion will be used for the repeated PK analysis. The mean concentration will be plotted against the scheduled sampling times. A tabulated summary with descriptive statistics will be given.

Immunogenicity: Anti-human FP-1305 antibodies will be assessed analysed by a validated method. Immunogenicity results will be summarized by listing of all available immunogenicity data. The frequency of positivity will be given by dose and cohort. The correlation of AEs and immunogenicity may be examined.

12.3 Exploratory outcome variables

The proportion of lymphocyte subsets (CD4, CD8, their ratio, NK-cells, B-cells and regulatory T-cells from CD127 FoxP3 assay) will be analysed at given time points with flow cytometry and plotted against the scheduled sampling time. The level of circulating cytokines and chemokines (these may include but are not limited to the following IFN α , IFN γ , IL-1 α , IL-1 β , IL-1RA, IL-2, IL-4, IL-5, IL-6, IL-7, IL-8/CXCL8, IL-9, IL-10, IL-12p70, IL-13, IL-15, IL-17A, IL-18, IL-21, IL-22, IL-23, IL-27, IL-31, TNF α , TNF β , GM-CSF, Eotaxin/CCL11, GRO alpha/CXCL1, IP-10/CXCL10, MCP-1/CCL2, MIP-1 α /CCL3, MIP-1 β /CCL4, RANTES/CCL5, SDF-1 α /CXCL12) will be analysed by multiplex assays pre- and post-treatment. Aggregated data (mean and median) from each dose level will be presented using descriptive statistics by tumour type cohort.

The change in LDH, LDL and OxLDL, CRP, CA-125 (OC subjects), CA19-9 (PDAC, gallbladder cancer, cholangiocarcinoma, gastric adenocarcinoma subjects), CEA (CRC, ER+ BC, gastric adenocarcinoma subjects), CA-15-3 (ER+ BC subjects) and AFP (HCC subjects) levels in the subjects pre- and post-treatment will be reported with descriptive statistics.

The immune cell profile, the level of circulating cytokines and chemokines, CLEVER-1 on circulating monocytes, IHC parameters (CD4 positive cells, CD8 positive cells, CD163 positive cells and FoxP3 positive cells), Clever-1 and PD-L1 staining parameters (intra-tumoral VCs/Positive viable cells/Combined positive score for STAB1, and Combined positive score for PD-L1) and possible genetic analyses during the first four cycles of treatment will be reported using descriptive statistics (by DCR and non-DCR, and in total) and visualizations. If feasible, exploratory statistical analyses will also be used to describe the associations.

Overall survival data, including but not limited to the six-month, one-year and two-year survival rates will be reported for each cohort, and will be analyzed using the Kaplan-Meier method and Cox-modelling where appropriate.

Progression free survival including but not limited to the six-month, one-year and two-year survival rates will be reported for each tumor type cohort and will be analyzed using the Kaplan-Meier method and Cox-modelling where appropriate.

Duration of response (CR, PR or SD) will be reported using descriptive statistics.

The association of tumor responses to survival will be explored by analyzing the overall survival based on the RECIST outcome at cycle 4 and cycle 7 (disease control subjects vs progressive disease subjects). This analysis will be done using a landmark analysis approach; thus the survival will be calculated from the planned tumor measurement time (cycle 4) and only those subjects who have not discontinued before this landmark time point will be included in this analysis. Also, the effect of the length of latest prior treatment line for the cancer to survival will be explored.

The length of latest prior treatment line will be also compared to length of treatment in this study, and summarized using descriptive statistics as a ratio.

13 PK variables

The PK profile of a single dose (during Cycle 1) and repeated doses (during Cycles 2-5) of FP-1305 will be determined by repeated measurements of the drug concentration in the circulation. Peak concentration (C_{\max}), trough concentration (C_{\min}), area under the serum concentration versus time curve (AUC), clearance, volume of distribution, and terminal halflife ($t_{1/2}$) for each dose level will be determined using noncompartmental analysis (NCA). PK parameters will be estimated using version 8.3 of Phoenix® WinNonlin® software (Certara USA, Inc., Princeton, NJ). Results will be presented using descriptive statistics by cycle and each tumour type will be reported separately.

Descriptive statistics for the concentrations by time will be presented using planned timepoints and imputing zero for values below lower level of quantification (LLOQ). NCA calculations will use actual timepoints applying the following rules:

- Actual time of the planned 0 h sample will be set to 0 h and actual times for other samples will be calculated relative to that
- LLOQ concentration values will be set missing

Phoenix® WinNonlin® will use the following settings to compute parameters:

- Linear trapezoidal linear interpolation calculation method
- Uniform weighting
- IV infusion dose
- Plasma model type
- Lambda Z Acceptance Criteria
 - o $Rsq_{\text{adjusted}} \geq 0.85$
 - o $\text{Span} \geq 3.0$ half-lives
 - o Includes ≥ 3 timepoints after T_{\max}

Selection of points used in the slope parameter calculations will be confirmed visually and may be adjusted if automatic selection of points is seen questionable.

14 Analysis of safety and tolerability

All subjects in the FAS-S analysis set (all subjects receiving study treatment) will be included in the safety and tolerability analysis.

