¹⁷ Predose assessment in Cycles 1, 2, 3 and 4. Post IMP administration timepoints in Cycles 1 and 2 D2 (+/- 4 h), D8 (+/- 24h) and D15 (+/- 24 h)

¹⁸ Predose assessment in Cycles 1, 2, 3 and 4. Post IMP administration timepoints in Cycles 1 and 2 D8 (+/-24 h) and D15 (+/- 24 h)

¹⁹ First tumour biopsy must be less than 6 months old from the date of consent or taken during the screening period. In addition, an archival block may be used if needed; the biopsy in Cycle 2 within 10 days after the IMP administration. Biopsy from new lesions is recommended if assessed feasible by the investigator considering the location of the lesions and condition of the subject.

²⁰ The same imaging method (CT, MRI) per subject must be used throughout the trial. First scan (C1) must be less than 6 weeks prior the first dose (routine diagnostic image can be used); the scans in other cycles within +/- 10 days from the IMP administration

²¹ Cycles 1, 4, 7, 10, and every third cycle thereafter, up to one year. If the treatment extends beyond one year, 18- (\pm 1 month) and 24- (\pm 1 month) month images are mandatory to take if not routinely taken at these timepoints. In addition to the imaging time-points specified here, also any other imaging performed by the site will also be collected.

²² Brain imaging (CT) for exclusion of CNS metastasis. Routine diagnostic image (CT/MRI) can be used if available. The brain scan within six weeks prior to the 1st dose is acceptable.

²³ First three subjects testing new doses or dosing frequencies in Part II should be closely monitored for safety for the first 24 h after the first IMP infusion and for a minimum of 6 h after the second IMP infusion at the trial site hospital. Other subjects in Part II will be monitored for a minimum of 6 h after the first IMP infusion. After Cycle 1 all subjects should be observed for a minimum of 2 h after the IMP infusions. In any part of the trial, post-dose observation will be longer if deemed appropriate. AE assessment done if visit indicated.

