8.3 Treatment Schedule

The treatment period is divided into cycles. Each cycle in Q3W dosing lasts three weeks (21 days). The IMP will be administered on Day 1 of each cycle (Q3W) for up to one year with the possibility to extend the treatment beyond one year according to routine clinical practice (see [Section 8.7.1](#)). If the IMP infusion cannot be administered as scheduled the IMP infusion must be administered as soon as possible. The IMP administration day is counted as Day 1 of the cycle (for delays see [Section 8.7](#)).

Protocol Addendum implements more frequent dosings (Q2W and Q1W). Protocol Addendum requires all relevant national approvals in the countries concerned prior to implementation.

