Response Category	Description
Complete Response (CR)	Disappearance of all non-target lesions
Incomplete Response/ Stable Disease (SD)	Persistence of one or more non-target lesion(s)
Progressive Disease	Appearance of one or more new lesions and/or unequivocal progression of existing non-target lesions ¹

Notes:

1. To achieve "unequivocal progression" on the basis of the non-target disease, there must be an overall level of substantial worsening in non-target disease such that, even in presence of SD or PR in target disease, the overall tumour burden has increased sufficiently to merit discontinuation of therapy.

C. Evaluation of Best Overall Response

The best overall response is the best response recorded from the start of treatment until disease progression. In general, the patient's best response assignment will depend on the achievement of both measurement and confirmation criteria.

D. Overall Responses for all Possible Combinations of Tumour Responses in Target and Non-target Lesions With or Without the Appearance of New Lesions

Target Lesions	Non-target Lesions	New Lesions	Overall Response
Complete response (CR)	CR	No	CR
Complete response (CR)	Non-CR/non-Progressive disease	No	PR
Complete response (CR)	Not evaluated	No	PR
Partial response (PR)	Non-Progressive disease	No	PR
Stable disease (SD)	Non-Progressive disease	No	SD
Not all evaluated	Non-Progressive disease	No	Not evaluable (NE)
Progressive disease	Any	Yes or no	Progressive disease
Any	Progressive disease	Yes or no	Progressive disease
Any	Any	Yes	Progressive disease

Patients with a global deterioration of health status requiring discontinuation of treatment without objective evidence of disease progression at that time should be classified as having "symptomatic deterioration." Every effort should be made to document the objective disease progression, even after discontinuation of treatment.

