Regarding Part II, the first three subjects recruited to the unique cohort are included in the DLT evaluable population. The amount is expanded to six subjects if there is one DLT event in the first three subjects. The following cohorts are investigated: Q3W cohorts at dose levels that have not previously been tested in Part I, Q2W cohorts at each new dose level and Q1W cohorts at each new dose level. DLT assessment period in Part II is 4 weeks from the first dose of FP-1305.

Efficacy evaluable population: Includes all subjects who have received at least one dose of FP-1305 for the first time and has tumour imaging conducted at the baseline, and at least once during the treatment or progress or die due to their disease before the first tumour imaging post FP-1305 administration. This formulates the Full Analysis Set for Efficacy (FAS-E).

In the FAS populations also Part I subjects will be included.

9 General statistical considerations

Summary statistics will include at least the number of subjects, mean, standard deviation, median, minimum and maximum for continuous variables, and frequencies and percentages for categorical variables. All data collected will be listed by subject.

In Part II, the disease group or dosing cohorts of 10 subjects will be presented separately as also the Simon's design rule will be applied separately for each cohort. In addition, the cohorts using originally recommended dosing regimen for Part II, Q3W (1.0 mg for all cohorts and 0.3 mg/kg and 3.0 mg/kg for colorectal adenocarcinoma), will form a population (originally enrolled part II cohorts). Also, a pooled population of Part I subjects (n=30) and Part II originally enrolled subjects (n=120) will be used for survival endpoints. The total number of subjects in this dataset is n=148 as there were 2 part I subjects (colorectal adenocarcinoma 0.3 mg/kg) included in Part II.

In the statistical analyses a p-value less than 0.05 will be considered as an indication of statistical significance. If not stated otherwise, all tests will be performed as two-sided tests and two-sided 95% confidence intervals will be produced. Missing values will not be imputed in the analyses.

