9.1 Handling of dropouts or missing data

Missing values will not be imputed.

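### The Part II landmark survival analysis uses RECIST status at Cycle 4 and Cycle 7 but states only a Cycle 4 clock and risk set; the size and direction of the bias depend on a grouping that SAP 12.1 and 12.3 leave unreconciled

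*SAP*

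**What the plan says.** Part II SAP section 12.3 explores the link between tumour response and survival by "analyzing the overall survival based on the RECIST outcome at cycle 4 and cycle 7 (disease control subjects vs progressive disease subjects". It calls this a landmark approach and gives one starting point and one inclusion rule: "the survival will be calculated from the planned tumor measurement time (cycle 4) and only those subjects who have not discontinued before this landmark" are kept. No clock or risk set is given for Cycle 7, and discontinuation is not defined as stopping treatment or leaving the study.

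Part II SAP section 12.1 has a rule meant for the analyses generally: "The same definition, CBR at cycle 4 or at cycle 7, will be used for the classification of subjects (DCR vs non-DCR". So section 12.1 says or and compares DCR with non-DCR. Section 12.3 says and, compares disease control with progressive disease, and does not cite section 12.1.

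Other relevant statements:
- Protocol 8.3: "Each cycle in Q3W dosing lasts three weeks (21 days".
- Protocol Table 2, imaging footnote: "the scans in other cycles within +/- 10 days from the IMP administration".
- Part II SAP section 9: "a pooled population of Part I subjects (n=30) and Part II originally enrolled subjects (n=120) will be used for survival endpoints". After removing two subjects counted twice this is 148, treated every three weeks.
- Part II SAP section 9.1: "Missing values will not be imputed".

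**The concern.** A landmark analysis is valid because each subject's group is known when the clock starts. If the group depends on a later scan, a subject placed by that scan has to survive to it, and that stretch of guaranteed survival is credited to the subject's group. This is the artefact that a landmark is chosen to prevent.

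Here the later scan falls three cycles after the only stated clock. The output is definite: a landmark table is in the planned table list (Part II SAP 20.1), section 9 reads p below 0.05 as an indication of significance, and section 9.2 foresees presentations and publications from ongoing data. A survival difference by disease control could be reported although part or all of it comes from the timing.

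**Working it through.** The documents give no hazard ratio (HR), event count or power for this analysis, so there is no figure of the plan's own to reproduce. The pooled count does reproduce: 30 + 120 − 2 = 148.

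**Gap between clock and second scan.** Cycle 4 Day 1 is 3 × 21 = 63 days after first dose; Cycle 7 Day 1 is 6 × 21 = 126 days. The gap is 126 − 63 = 63 days. The clock starts at the planned Cycle 4 time, so only the Cycle 7 window varies: 63 ± 10 gives 53 to 73 days.

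**Assumptions.** The documents give no survival or control rates for this population. I assume exponential survival with median m = 5, 7, 9 or 12 months, tumour status unrelated to survival (true HR 1.00), a proportion c = 30% or 50% controlled at Cycle 4, and a proportion r = 50%, 60% or 70% of those still controlled at Cycle 7 if alive. Survival follow-up ends two years after first dose, that is 730 − 63 = 667 days after the Cycle 4 clock.

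**Deaths in the gap.** The probability of surviving 63 days is 2^(−63/(30.4 m)):
- m = 5: 2^(−63/152) = 0.751, so 25% die in the gap.
- m = 12: 2^(−63/365) = 0.887, so 11% die.

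A subject classed by the Cycle 7 scan cannot be among these deaths.

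**Share of the control group with guaranteed time.** Take m = 5 and c = 30%.
- Control at either cycle, with 10% of Cycle 4 progressors alive at Cycle 7 first controlled then: 0.70 × 0.10 × 0.751 = 0.053 of the risk set enters the control group late, out of 0.30 + 0.053 = 0.353. The share is 15%. With no late entrants it is zero.
- Control required at both cycles: every subject in the control group has the guaranteed 63 days, a share of 100%.

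**Null hazard ratios on the Cycle 4 clock.** For each grouping I wrote the numbers at risk A1(t), A0(t) and the deaths D1(t), D0(t) in the two groups, and solved ∫[D1 − (D0 + D1)·HR·A1/(HR·A1 + A0)]dt = 0 from 0 to 667 days.

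| Grouping | Null HR, control vs comparator |
|---|---|
| Cycle 4 status only | 1.00 |
| Control at Cycle 4 or 7 (section 12.1), no late entrants | 1.00 |
| Same, 2% of Cycle 4 progressors alive at Cycle 7 first controlled then | 0.985–0.994 |
| Same, 5% | 0.965–0.985 |
| Same, 10% | 0.934–0.971 |
| Section 12.1 rule, 20% lack a Cycle 4 scan, their deaths before Cycle 7 counted as non-DCR | 0.91–0.96 |
| Same, those deaths left out | 1.00 |
| Control at both vs progression at either; Cycle 4-controlled subjects who die before Cycle 7 unclassified | 0.78–0.89 |
| Control at both vs all others | 0.68–0.83 |
| Cycle 7 progression overrides Cycle 4 control; earlier deaths stay in the control group | 1.08–1.32 |
| Cycle 7 scan required in both groups | 1.00, but both curves contain the 63 days |
| Cycle 7 status on a Cycle 7 clock and risk set | 1.00 |

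**False-positive rate** (simulated trials, 148 subjects before the landmark, two-sided 5% test): 5–6% under the section 12.1 rule with 10% late entrants; 5–14% for control at both versus progression at either; 4–6% when status and clock match.

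**The case against.** The strongest reply is that section 12.1 already supplies the classification. A subject controlled at Cycle 4 who dies before Cycle 7 meets the either-cycle rule and is DCR, so a reader who infers that the SAP has no rule for this subject goes too far. Nor does the no-imputation statement remove someone already classified. Under that rule only late entrants carry guaranteed time, and the bias is small. This stands, and it is why no single HR such as 0.8 can be presented as what the plan will produce.

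A reader might also infer that the analysis necessarily favours disease control. The documents do not support that: one admissible grouping pushes the HR above 1, and others leave it at 1.00.

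Two separate landmarks may have been intended. If so, the second clock and risk set are simply not written.

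Three things remain. Section 12.3 does not cite section 12.1, uses a different conjunction and names a different comparator, so a programmer could choose any of several groupings. Late control cannot be dismissed: Protocol Appendix 1 says "The best overall response is the best response recorded from the start of treatment until disease progression", but that defines best overall response and not status by cycle, while Protocol 8.4.7 anticipates pseudoprogression and 8.10 allows treatment beyond progression. And even the section 12.1 rule is not free of bias when Cycle 4 scans are missing and early deaths count as non-DCR.

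**Conclusion.** The defect is real but minor. Section 12.3 uses Cycle 7 status with a clock and risk set stated only at Cycle 4, 63 days earlier, and sections 12.1 and 12.3 must be reconciled. The null HR is about 0.93 to 1.00 under the section 12.1 rule with up to 10% late entrants, about 0.91 to 0.96 under that rule if a fifth lack a Cycle 4 scan and their early deaths count as non-DCR, about 0.7 to 0.9 if control must hold at Cycle 7, and about 1.1 to 1.3 in the opposite direction if Cycle 7 progression overrides.

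Every one of these values rests on assumed survival and control rates; what the documents fix is the gap. The consequence is low: section 12.3 presents the analysis as exploration, section 16 calls all the SAP's analyses exploratory, and expansion to Part III rests on a clinical benefit rate of 1/10 (sections 7 and 12.1).

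**What to change.** In section 12.3:
- For the Cycle 4 landmark, classify on Cycle 4 status alone, with the Cycle 4 clock and risk set.
- Run any Cycle 7 comparison as a separate landmark with its own Cycle 7 clock and risk set.
- Do not use the combined class of section 12.1 with a Cycle 4 clock, and say in section 12.1 that its rule does not apply here.
- Replace the discontinuation criterion by: alive and in survival follow-up at that landmark, with a documented RECIST status by then. Progression documented earlier keeps a subject in the progressive-disease group. Report how many subjects are left out.

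The cost is SAP wording, one extra table and minor programming. The Cycle 7 landmark has fewer subjects: if all 148 are followed, about 148 × 0.751 = 111 to 148 × 0.887 = 131 are alive at Cycle 4. Applying the same factor again leaves about 83 to 116 at Cycle 7, so about 15 to 28 deaths fall between the landmarks. Starting each clock at the end of its scan window, or adding a Cox model with time-dependent disease control, is a matter of preference and not part of this fix.
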